Subjects will be asked to come in for a total of two study visits (baseline and follow-up) and self-administer nVNS/sham twice a day for a period of 7 days in between these visits. During both visits, subjects will be asked to complete behavioral assessments and to participate in an fMRI scan. If subjects are unable to come in for their follow-up person, they will be given the option to complete the questionnaires remotely (via telehealth, phone, or mail). Procedures for this are detailed under "Covid-19 adaptations". Please see figure below for a schematic and chronological presentation of the research components. Subjects will be randomly assigned to receive nVNS or sham stimulation prior to performing a well-validated fMRI task designed to assess the neural correlates of

physical distress (pain processing via heat stimulus). During each scan (baseline and follow-up), nVNS or sham stimulation will be administered once for 120 seconds. Subjects will remain in the same condition (sham/nVNS) assigned at baseline and be instructed to self-administer nVNS/sham at home for 7 days and return for a follow-up visit (treatment adherence and adverse events will be measured with a daily log and interview). Behavioral assessments of functional disability, quality of life, psychological and physical distress and craving will be administered at baseline, after stimulation, and at follow-up (post 7 days of nVNS/sham self-administration). After completion of the study visit, subjects will be evaluated for any side effects from stimulation and sent home. The patient will be instructed to carry out stimulation (sham or nVNS) twice a day for the following 7 days. Subjects will be instructed to drink "as usual" during the 7-day treatment window, with the intention to observe whether nVNS leads to reduced alcohol use, and will be asked to abstain again for 24 hours prior to their follow-up study visit on day 9 (allowing subjects to administer nVNS/sham on day 8 ad lib). Drinking behavior during the trial (as well as at baseline and follow-up) will be quantified with the Timeline Follow Back. Treatment acceptability will be assessed at follow up. We previously established feasibility of applying nVNS/sham in healthy individuals (Lerman et al., 2019) and have completed similar work with Veterans. However, this work has not been done in heavy drinkers.

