Description of nVNS device: The gammaCore® is a multi-use device designed for intermittent external stimulation of the vagus nerve, capable of delivering multiple (up to 150) 90-second vagal nerve stimulation with a 30-second margin for set-up and operator adjustment of the stimulation intensity (the stimulation automatically stops 120 seconds after the device is powered on). The user applies conductive gel to the stimulation surfaces and then holds the gammaCore® device on the skin over the vagus nerve of the neck (between the trachea and the sternocleidomastoid muscle, over the carotid pulse). The gammaCore® device produces a proprietary, low voltage electric signal that generates an electric field in the vicinity of the vagus nerve when the device is placed in the intended location. The sham stimulation is comprised of very low voltage direct current (DC) as opposed to alternating current used in the nVNS device.

For self-administration, the subject will undergo transcutaneous electrical stimulation over the neck in with the gammaCore device. Prior to stimulation, the subject will place gel on the device contacts and then place the device to the neck, after which the thumbwheel is turned to increase the stimulation intensity until the subject feels a buzzing sensation. This sensation will occur for 2 minutes after which the device automatically turns off. This will be repeated 1 time during visit #1 and #2. Between visit #1 and visit #2, stimulation will be carried out at home once daily for 7 days.

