There is discernable difference in stimulation of sham vs. nVNS in that nVNS does cause muscle contraction (Platysma). To minimize any Placebo or Nocebo effects, all devices (nVNS and sham) will have an identical appearance and all subjects will undergo identical training paradigms. Both sham and active nVNS treatment produce reliable sensation on subject skin (sham device delivers a low dose DC voltage signal that results in paresthesia and prickling like sensation) and in our preliminary survey, subjects are unable to differentiate sham from active nVNS device ($p>.1$). Written home instructions are provided for use of both devices. Both devices are handheld and easily applied to the neck (over the carotid artery) for a treatment of two minutes (once daily for seven days). The nVNS device produces a low-voltage electrical signal (5-kHz sine wave series that occurs for 1 ms and repeated every 40 ms [25 Hz]). The sham device is identical in appearance, and carries out the same period of stimulation but differs in stimulation parameters with a slowly varying direct current(DC) signal(0.1 Hz) that produces a slight skin tingling sensation. In both the nVNS and sham device, there is an initial 30-sec ramp up period, resulting in a total of 90 sec of actual stimulation per two-minute stimulation session. There is a knob on both sham and nVNS device that is turned to the on position. As stated above, the stimulation occurs for 2 minutes time after the knob is turned on. For sham device the intensity is titrated (via the rolling knob) until there is actual sensation on the skin. For active nVNS device the intensity is increased until there is muscle (platysma) contraction. Finite element electric field modeling show at this intensity (with muscle contraction) the electric field penetrates deep and activates the vagus nerve.

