distress, and alcohol craving in Veterans with AUD, and if nVNS alters neural activation patterns in brain regions involved in perception and awareness of distress. The family-wise error (FWE) rate will be set at $p=.05$ as we have limited power to more stringently correct for multiple comparisons. We will examine correlations between dependent variables and potentially confounding factors, such as age, AUD severity, or level of depression and anxiety, and covary for these factors if necessary. In addition, we will covary for TLFB data (i.e., days since last drink, number of drinks, percent days drinking, etc.).

Aim 1: The primary aim is to establish feasibility and acceptability of using nVNS as a rehabilitative treatment for AUD in Veterans within the VA San Diego Healthcare System (VASDHS).

To test hypothesis 1: Recruiting 16 subjects within 12 months as well as treatment adherence and retention rates of $>75\%$ will be considered feasible. A mean group score for treatment acceptability (TAQ) will be calculated for the nVNS group and a value of ≥ 5 will be considered an acceptable treatment (17).

Aim 2 (exploratory): The secondary aim is to evaluate preliminary effectiveness of nVNS in improving functional outcomes and quality of life, as well as in reducing distress and alcohol craving.

To test hypothesis 2a: We will use linear mixed effects (LME) models to assess the impact of treatment group on Substance Use Recovery Evaluator (SURE) and WHOQOL-BREF scores. Specifically, we will test group (nVNS/sham) by time (baseline/7 days FU) interactions.

To test hypothesis 2b: We will use LME models to assess the impact of treatment group on Beck Anxiety Inventory and PROMIS Pain Interference Scale scores. Specifically, we will test group (nVNS/sham) by time (baseline/7 days FU) interactions.

To test hypothesis 2c: We will use LME models to assess the impact of treatment group on Alcohol Urge Questionnaire scores. Specifically, we will test group (nVNS/sham) by time (baseline/7 days FU) interactions.

Aim 3 (exploratory): The final aim is to alter neural activation patterns in brain regions subserving perception and awareness of emotional and physical distress using nVNS.

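### The primary adherence criterion (above 75%) rests on the subject's log and interview alone, with no planned objective check and no stated unit or settled denominator

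*Combined protocol and SAP*

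**What the plan says.** The Data analysis section restates Aim 1 as primary: "The primary aim is to establish feasibility and acceptability of using nVNS as a rehabilitative treatment for AUD in Veterans". Under hypothesis 1, the feasibility rule adds to a recruitment target that "treatment adherence and retention rates of $>75\%$ will be considered feasible". It does not say whether the adherence rate applies to each subject, to all sessions pooled, or to the share of subjects who adhere.

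The source of the adherence data appears once, in Design and Methods (Approach): "treatment adherence and adverse events will be measured with a daily log and interview". No read-out, return check or comparison with the device is described.

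The number of planned home sessions is stated in two ways. The Approach has subjects "self-administer nVNS/sham twice a day for a period of 7 days", and the Study outline agrees. The Description of nVNS device says that "stimulation will be carried out at home once daily for 7 days", and repeats once-daily use later in the same section. The Approach also allows ad lib use on day 8. On device capacity, the description says only that the device is "capable of delivering multiple (up to 150) 90-second vagal nerve stimulation".

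**The concern.** A feasibility study exists largely to find out whether people use the device at home as asked. Here the figure that answers this comes only from the people whose use is in question. An interview lets staff query the log, but it is still self-report. For drinking, the plan labels the Timeline Follow Back as self-report and uses a breathalyzer at visits. For adherence it gives neither a caveat nor a check.

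Sessions entered but not done can raise the rate and cannot lower it. With only 7 or 14 planned sessions per subject, each entry carries much weight. At stake is whether a statement that adherence exceeded 75% can be taken at face value when a larger trial is considered. A lesser consequence is that, if Aim 2 or Aim 3 shows no effect, low real exposure would be hard to tell from no effect.

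**Working it through.** The 75% cut-off is a chosen value and the documents derive no figure for adherence, so there is nothing to reproduce. The check is how far false entries can move the criterion under each possible unit.

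**Inputs.** Threshold: above 75% (Data analysis, Aim 1). Home sessions: 2 × 7 = 14 (Approach, Study outline) or 1 × 7 = 7 (Description of nVNS device). Subjects: 20, 10 per arm (Human Subjects). Recruitment target: 16 (Aim 1). Capacity: up to 150 stimulations, with one stimulation at each of two visits (Description of nVNS device).

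**1. Per-subject unit.** The smallest k with k/n > 0.75 is:
- n = 14: 10/14 = 71.4% fails and 11/14 = 78.6% passes, so k = 11.
- n = 7: 5/7 = 71.4% fails and 6/7 = 85.7% passes, so k = 6.

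| Sessions done | True rate | Plus 1 entry | Plus 2 entries |
|---|---|---|---|
| 10 of 14 | 71.4% | passes | passes |
| 9 of 14 | 64.3% | fails | passes |
| 8 of 14 | 57.1% | fails | fails |
| 5 of 7 | 71.4% | passes | passes |
| 4 of 7 | 57.1% | fails | passes |
| 3 of 7 | 42.9% | fails | fails |

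Only subjects one or two sessions short are affected. As an illustration, assume independent sessions and a true session rate of 60% to 75% (neither is in the documents). The binomial probability that a subject passes is then:

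| True rate | n = 14: truthful / +1 / +2 | n = 7: truthful / +1 / +2 |
|---|---|---|
| 60% | 0.124 / 0.279 / 0.486 | 0.159 / 0.420 / 0.710 |
| 65% | 0.220 / 0.423 / 0.641 | 0.234 / 0.532 / 0.800 |
| 70% | 0.355 / 0.584 / 0.781 | 0.329 / 0.647 / 0.874 |
| 75% | 0.521 / 0.742 / 0.888 | 0.445 / 0.756 / 0.929 |

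**2. Sessions pooled over 20 subjects.** The totals are 20 × 14 = 280 (211 needed) or 20 × 7 = 140 (106 needed).
- Two entries by one subject: 2/280 = 0.71 points or 2/140 = 1.43 points.
- One extra entry by every subject: 1/14 = 7.1 points or 1/7 = 14.3 points. A true rate above 75 − 7.1 = 67.9% or 75 − 14.3 = 60.7% would then be reported as above 75%.
- If only the 10 nVNS subjects count, one subject's two entries move the rate by 2/140 = 1.43 or 2/70 = 2.86 points. The effect of one entry per subject is unchanged.

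**3. Share of adherent subjects.** Above 75% needs 16 of 20 (15/20 is exactly 75%), or 13 of 16. Each subject must first be classed as adherent or not. If the same 75% cut is used for that, step 1 applies, and a few near-threshold subjects could decide the result.

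**4. What the stated capacity can show.** 150 − 14 − 2 = 134 stimulations remain, or 150 − 7 − 2 = 141. No subject would come near the limit, so the limit itself reveals nothing about missed sessions. Only a readable record of use would.

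**The case against.** The strongest reply is that this is a preference for objective monitoring in a 20-subject, 7-day pilot, and that the objective source may not exist. Much of that reply is fair, and it rules out three stronger readings.

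- A reader might infer that one or two entries turn a failing subject into a passing one as a general matter. The plan states no per-subject rule, and even under such a rule only near-threshold subjects change.
- A reader might infer that the plan neglects a counter it already has. The documents give a capacity, not a display or a read-out, and give it for the gammaCore. They do not say that the sham device has the same limit or any count.
- A reader might put a figure on over-reporting, say 10 to 20 points. The documents give no basis for one. Moreover, 65% plus 10 points is exactly 75%, which does not exceed the threshold.

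Other parts of the reply also stand. Sessions done but not logged would lower the rate, so the net error is not certain to be upward. Aims 2 and 3 are labelled exploratory in the Data analysis section, and no adherence-based analysis is planned, so the consequence there is minor. A device total cannot date sessions: day 8 use could stand in for missed sessions. It would show activation but not placement or intensity. Subjects followed up remotely may not return the device at a visit.

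What the reply does not remove is the core. A primary criterion with a numerical cut-off has self-report as its only stated source. If no count is available, the wording of the conclusion should say so.

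**Conclusion.** The point holds in limited form. The adherence criterion is measured by self-report alone, with no planned check, and false entries act in the direction of feasible. If the unit is the subject, one or two entries decide the outcome for those at 9–10 of 14 or 4–5 of 7 sessions. If sessions are pooled over 20 subjects, one person's entries hardly matter (at most 1.4 points), but a habit shared by all subjects does: 7.1 or 14.3 points for a single extra entry each.

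These sizes follow from the session counts and the threshold. They say what false entries would do, not how many there will be; the documents do not allow an estimate of that. The pass probabilities rest on assumed rates and independent sessions and are illustrative only. Whether a device check is possible depends on a feature that the documents do not confirm. The weakness does not invalidate the trial, but it bears on a primary conclusion and is cheap to address.

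**What to change.** 1. State the unit of the adherence rate (per subject, pooled sessions, or share of adherent subjects), which subjects count, and how day 8 use and missing logs are handled.
2. Reconcile the once-daily and twice-daily statements so that the denominator is fixed. No log or device count becomes a percentage until this is done.
3. Confirm whether the active and sham devices both show a use count or remainder.
4. If both do, record it at hand-over, after the visit 1 stimulation, and at return, before any follow-up stimulation. For remote follow-up, record it whenever the device comes back. Credit each subject with the lower of the log count for the prescribed days and the device difference, and report log-versus-device disagreement by arm.
5. If a count cannot be read in both arms, report the criterion and the feasibility conclusion as self-reported adherence.

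The cost is two readings per subject and a few lines in the plan. The adherence rate may come out lower and a few readings may be missing. Taking the lower figure limits over-reporting but does not recover sessions that were done and not logged. Day 8 use can still mask some missed sessions, and a count shows activation, not correct placement.

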Subjects will be asked to refrain from drinking alcohol for 24 hours prior to each study visit as symptoms of anxiety, irritability, and physical distress due to the cessation of heavy drinking typically occur during this time frame (Caputo et al., 2020). A breathalyzer will be used to at each study visit to ensure subjects are not intoxicated. Subjects who test positive will be rescheduled for a later session and monitored until BAC returns to safe levels. During the 7-day window between study visits, subjects will be asked to abstain from drinking for 24 hours prior to each visit. The timeline-followback (TLFB) will be used to quantify alcohol consumption prior to each visit. The TLFB is a self-report measure. Subjects with severe alcohol withdrawal will not be included in the study. Therefore, no management of alcohol withdrawal symptoms will be needed during the study. In order to ensure subject safety and prevent medical complications due to acute withdrawal syndrome, two measures will be put in place: 1) During the screening process, subjects will be asked if there has been a time in the past where they did not drink for 48 hours and if they experienced any symptoms or complications during that time, and 2) subjects with a score higher than 9 on the Clinical Institute Withdrawal Assessment for Alcohol Scale (CIWA-Ar) will be excluded from the study and immediately referred to the hospital as it may not be safe for these individuals to abstain from alcohol without medical supervision.

Study outline:

Baseline Visit

1. Behavioral assessments (see below)
2. fMRI scan
 - nVNS/sham (during scan)
 - Scans: Anatomical, Heat pain task

7 day interval: at home

nVNS/sham self-administration (2 x day for 7 days)

Follow-up Visit

1. Behavioral assessments (see below)
2. fMRI scan
 - nVNS/sham (during scan)
 - Scans: Anatomical, Heat pain task

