3. Able to forgo consumption of alcohol for 24 hours without any serious discomfort including nausea/vomiting, visual/auditory/tactile hallucinations, or non-essential tremor.
4. Capable of complying with study schedule, procedures, and speaks English.
5. Able to provide voluntary written informed consent prior to initiation of visit 1; and be able to commit to the return visit at the end of the study.

Exclusion Criteria.

1. Clinical Institute Withdrawal Assessment of Alcohol Scale (CiWA) score ≥ 9 on the day of the scan (symptoms judged to be due to co-existing anxiety conditions or headache disorders will not be counted toward the total).
2. Currently or recently (within last 90 days) enrolled in abstinence-based treatment program.
3. Evidence of a maladaptive pattern of substance use or abuse (based on the SCID) other than alcohol one month prior to the screening visit.
4. Significant mental illness, e.g. psychosis or

bipolar disorder based on SCID interview. We will not exclude for PTSD 5. At risk for suicide or homicide (based on BDI-2 screen and follow-up clinical interview). 6. History of neurological disorder that might be associated with cognitive dysfunction. 7. History of head trauma involving loss of consciousness >24 hours and post-traumatic amnesia of more than 1 week. 8. Chronic pain as defined by pain persisting beyond its ecological alerting function, and clinically defined as lasting longer than 3 months, and/or currently under the care of a chronic pain physician. 9. Clinically significant uncontrolled/unstable medical illness or clinically significant surgery within 1 month of the screening visit. 10. MRI-related exclusion criteria: cardiac pacemaker, metal fragments in eyes/skin/body, aortic/aneurysm clips, hearing aid, heart-valve replacement, copper intrauterine device, shunt (ventricular or spinal), neuro/bio-stimulators, inability to lie still on their backs for 60 minutes, piercings that cannot be removed. Any implants will be reviewed for safety. 11. Vagus nerve stimulation related criteria: history of carotid endarterectomy, severe carotid artery disease (e.g. history of transient ischemic attack (TIA) or stroke], congestive heart failure, cardiac arrhythmia, known severe coronary artery disease or recent myocardial infarction (within 5 years), or history of seizure or syncope (within the last 1 year), prior neck surgery.

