Subjects with a score higher than 9 on the Clinical Institute Withdrawal Assessment for Alcohol Scale (CIWA-Ar) will be excluded from the study and immediately referred to the hospital as it may not be safe for these individuals to abstain from alcohol without medical supervision.

Data analysis

Image analysis pathway: Image processing will be done with the AFNI software package (afni_proc.py). Specifically, the EPI timeseries despiked (3dDespike), slice time corrected (3dTshift), and co-registered, which will provide motion parameters (x, y, z, roll, pitch, yaw) for each EPI image's registration to the optimal base image (align_epi_anat.py:3dvolreg). Based on the distribution of these average motion parameters, subjects will be excluded if the average in any one of these parameters exceeds 2 absolute deviations from the mean. All EPI timeseries will be moved to MNI coordinates (align_epi_anat.py: 3dQWarp), blurred to 2x voxel width (to account for individual variations in the anatomical landmarks (3dBlurToFWHM), and converted to percent signal change (3dcalc). Preprocessed time series data for each individual will be analyzed using a multiple regression model. A multivariate regressor approach will be used to relate changes in EPI intensity to differences in task characteristics. Regressors of interest include: 1) Pain [i.e., what activates during pain stimuli], 2) Non-pain [i.e., what activates during non-painful stimuli], 3) Pain anticipation [i.e., what activates during anticipation of pain stimuli] and 4) Non-Pain anticipation [i.e., what activates during anticipation of non-painful stimuli]. To reduce the false positives induced by auto correlations of the time series, data will be fit using the AFNI program 3dREML. Statistical analysis of fMRI derived data will be obtained with standard statistical techniques.

Group analyses. Statistical analyses will be performed to evaluate treatment acceptability, if nVNS improves functional outcomes, quality of life, emotional and physical

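### The CIWA-Ar exclusion cut-off is 9 or above in exclusion criterion 1 but above 9 in the withdrawal-safety text, so a score of exactly 9 is handled inconsistently

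*Combined protocol and SAP*

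**What the plan says.** The cut-off appears in three places in the combined protocol and SAP.

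- **Human Subjects, Exclusion Criteria, item 1.** A subject is excluded for a CIWA-Ar "score ≥ 9 on the day of the scan". A scoring rule is attached: "symptoms judged to be due to co-existing anxiety conditions or headache disorders will not be counted toward the total".
- **Design and Methods, the paragraph on 24-hour abstinence before the study outline.** As the second of two named safety measures, "subjects with a score higher than 9 on the Clinical Institute Withdrawal Assessment for Alcohol Scale (CIWA-Ar) will be excluded from the study", with immediate referral to hospital.
- **The paragraph directly after the exclusion list, before Data analysis.** The same sentence is repeated: subjects scoring higher than 9 "will be excluded from the study and immediately referred to the hospital".

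Neither of the last two mentions the scoring rule in criterion 1 or gives a time point for the score. The CIWA-Ar entry under Screening questionnaires describes the scale but gives no cut-off. Nothing says which statement governs.

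**The concern.** The trial asks heavy drinkers to abstain for 24 hours before each visit, and it relies on exclusion in place of treating withdrawal. The Design and Methods paragraph says "Subjects with severe alcohol withdrawal will not be included in the study" and continues "Therefore, no management of alcohol withdrawal symptoms will be needed during the study". CIWA-Ar is one of the two measures that paragraph names for preventing complications, and the only one with a numeric cut-off. Staff need one value to apply, and a monitor needs one value to check against.

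As written, someone who uses the safety text as the operating rule finds exclusion starting above 9. A subject scoring 9 could then be admitted in apparent compliance with that text and in breach of exclusion criterion 1.

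**Working it through.** This is a comparison of text; the plan gives no computed figure to reproduce. The inputs are the three statements above, and whole-number totals are assumed.

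**Step 1: the cut-offs side by side, with nothing discounted.**

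| CIWA-Ar total | Exclusion criterion 1 (≥ 9) | Safety text, both places (> 9) |
|---|---|---|
| 8 or less | not excluded | no action stated |
| exactly 9 | excluded; referral not mentioned | no action stated |
| 10 or more | excluded; referral not mentioned | excluded and referred |

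Every total above 9 is also at least 9, so the safety text excludes nobody whom criterion 1 would keep. The only total that meets ≥ 9 without meeting > 9 is 9 itself.

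**Step 2: can the statements be reconciled?** Yes, by treating them as cumulative: exclude from 9, refer above 9. But both safety sentences attach exclusion itself, not only referral, to a score higher than 9, and no sentence sets out two tiers. The reader has to supply that reading.

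**Step 3: the discounted total.** Take a raw total of 12 that falls to 7 once the symptoms named in criterion 1 are left out. Criterion 1 does not exclude, since 7 < 9. If the safety text also uses the discounted total, it takes no action, since 7 is not above 9. If it uses the raw total, the subject is excluded and referred, since 12 > 9. For referral, the answer matters for any raw total of 10 or more whose discounted total is 9 or less. The plan does not say which total the safety text means.

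**Step 4: effect of aligning the wording.** Criterion 1 already excludes all totals of 9 or more, so changing the safety text to ≥ 9 adds nobody to those whom criterion 1 excludes. If referral moves with it, the only total newly referred is 9.

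**The case against.** The strongest reply is that exclusion criteria are cumulative: meeting any one is enough. The safety sentences say what happens above 9; they do not say that a subject at 9 is eligible. Silence is not a contrary instruction, and the stricter rule stands in the numbered criteria list, where eligibility is normally decided. The safety sentences also omit the scan-day time point, so they read more like summaries than rival definitions. This reply stands in part. A reader might infer an outright contradiction at 9, and the documents do not support that, because all three statements can be followed at once. What remains is that the safety text presents above 9 as the exclusion threshold, twice, without saying that a stricter one applies.

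A reader might also infer that the raw and discounted totals give contradictory rules. That goes too far. The second safety sentence directly follows the exclusion list and may simply carry over the scoring rule in item 1. Nothing in the safety text specifies a raw score.

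A third tempting step is to say that the discount is bound to matter because the plan expects anxiety during abstinence. The plan does say that "symptoms of anxiety, irritability, and physical distress due to the cessation of heavy drinking typically occur during this time frame", but that is anxiety caused by stopping drinking. Criterion 1 sets aside only symptoms attributed to a separate anxiety or headache disorder. On its words, the discount does not remove the anxiety that the plan expects.

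Finally, other safeguards exist: the screening question about a past 48-hour period without drinking, and inclusion criterion 3 on tolerating 24 hours of abstinence. They reduce the consequence of a misread cut-off but do not settle what it is.

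**Conclusion.** The point holds as a minor inconsistency in a safety and eligibility threshold. The wording difference is certain. Its numeric reach is one score, 9, assuming whole-number totals and the same scoring basis in all three places. Whether the discounted total governs referral is a separate, secondary ambiguity.

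The documents give no distribution of CIWA-Ar scores, so the number of subjects affected cannot be estimated, and no claim is made that anyone would be wrongly enrolled. The planned 20 subjects (10 per arm) and all analyses are unaffected.

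**What to change.** 1. In the Design and Methods safety paragraph and in the paragraph after the exclusion list, change the exclusion threshold to a CIWA-Ar score of 9 or above, matching exclusion criterion 1.
2. State whether a score of exactly 9 also triggers hospital referral. Exclusion and referral share one sentence in both places, so changing the number alone would also refer a subject at 9. If the investigators want referral to stay above 9, the text should separate the two actions. That is a clinical choice for them.
3. State once whether the discounted total in criterion 1 also governs referral.

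The cost is a short wording amendment. CIWA-Ar is already administered and takes 5 minutes, so no procedure is added. Relative to criterion 1 nobody new is excluded by the aligned cut-off. At most, subjects scoring exactly 9 would also be referred, if the investigators choose that under item 2.
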